9.4 Data Analyses

9.4.1 Primary outcome.

To examine gait speed during W and WWT we will use repeated-measures analyses that include time of test (pre and post), and trial type (W or WWT) as within subjects factors, and imagery condition (imagined gait or AC) as the between-subjects factor. Consideration of these analyses will focus on the three-way interaction between time of test, trial type, and imagery condition.

9.4.2 Secondary and tertiary outcomes.

Similar repeated-measures analyses will be used for our secondary outcomes measures/additional EF measures: Trail Making Test, the Letter Number Sequencing Test, the Stroop Color and Word Test, and the Flanker Interference Task. These measures include the time to complete Trails B corrected for Trails A from the Trail Making Test (Trails B-A), the raw score from the letter-number sequencing task WAIS-III, the raw response time to Color-Word (incongruent) trials corrected for Color (congruent) trials from the Stroop Color and Word Test (i.e., Stroop Interference) and the flanker interference response time measure (incongruent-congruent trials) from the Flankers interference task. Although three of these four measures are difference scores, our analyses will be completed on raw scores in order to maximize power. More specifically, for these measures we will use repeated-measures analyses that included time of test (pre and post) and trial type as within subjects factors, and imagery condition (imagined gait or AC) as the between-subjects factor. Trial type for the Trail Making Test will be Trails A and Trails B. Trial Type for the Stroop Color and Word Test will be congruent trials and incongruent trials. Finally, trial type for the Flanker task will be congruous and incongruous trials. Consideration of these analyses will focus on the three-way interaction between time of test, trial type, and condition. Analyses will focus on the primary outcome variables during training and to the end of training period.

All behavioral analyses will be corrected for multiple comparisons using the Bonferroni correction.

We will use a whole-brain multivariate Ordinal Trend Covariance Analysis (OrT-CVA) to analyze the BOLD signal during imagined walking and walking while talking (66, 67). This is because we are interested in determining how the use of the entire locomotion and executive

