Age, sex and education will be covariates in all analyses. Given that is a pilot RCT on a fairly small sample of participants, it is not statistically feasible to control for more than the basic covariates listed above. Additional variables/potential covariates will be recorded and carefully examined for potential inclusion as covariates or outcome measures in upcoming full-scale RCT, including stride length (cm), double support time (s), cadence (steps/min), swing time (s), stance time, stride length variability (SD), swing time variability (SD), the Geriatric Depression Scale (54), Medical Illnesses and Medication questionnaires (26, 55), Cognitive and Physical leisure activity questionnaire (56-58), Falls (59), Smoking and alcohol consumption questionnaires, Obesity (assessed with weight, waist circumference, and BMI (kg/m²)), Vision (Snellen's chart), Disability (7 ADLs using the scale developed by Gill and colleagues (60, 61), IADL (62, 63), Blood pressure (Sitting/Standing), Gray Matter Volume/Atrophy (T1-Weighted structural images) White Matter Integrity (Diffusion Tensor Imaging; DTI) and White Matter Hyper intensities (Fluid-Attenuated Inversion Recovery; FLAIR).

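### Section 9.4.2 analyses Trails, Stroop and Flanker on raw scores for power, but its three-way interaction is the same test as the one on the difference score, so the stated gain is zero

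*Combined protocol and SAP*

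**What the plan says.** Section 9.4.2 names four executive-function measures. Three are difference scores: Trails B minus A, Stroop interference and Flanker interference. The fourth, Letter Number Sequencing, is a single raw score. For the three, the plan states: "Although three of these four measures are difference scores, our analyses will be completed on raw scores in order to maximize power".

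The model is a repeated-measures analysis with "time of test (pre and post) and trial type as within subjects factors, and imagery condition (imagined gait or AC) as the between-subjects factor". Each test has two trial types. The first is defined thus: "Trial type for the Trail Making Test will be Trails A and Trails B". The other two tests follow the same pattern, with an easier (congruent) and a harder (incongruent) level each.

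The effect of interest is also fixed: "Consideration of these analyses will focus on the three-way interaction between time of test, trial type, and condition". The section closes with "Age, sex and education will be covariates in all analyses" and says the sample is too small to control for more than these.

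For these outcomes the plan names no mixed model, pooled error term or covariance structure, and it gives no figure for the power gain.

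**The concern.** A raw-score analysis can be more powerful than a difference-score analysis if it tests a different effect or uses a different error term. Here the plan tests the one effect that rebuilds the difference score. The reason it gives for the choice then fails, and the analysis it adopts is the one it says it is replacing.

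Section 9.1.2 uses these tasks to look for far transfer and to choose outcome measures for later studies. If the analysis is described as maximising power, a null result may be given more weight than it deserves when outcomes are chosen for the full-scale trial. A more precise analysis of the same quantity is available from data already collected.

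**Working it through.** **The plan's own figure.** There is none for the raw-versus-difference choice. The nearest is n = 34 in section 9.2, for the same kind of three-way interaction in gait speed (alpha 0.05, power 0.80, f = 0.25). The correlation among repeated measures is not stated; assume 0.5. With two groups and m = 2 measurements:

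- noncentrality = f² × N × m / (1 − ρ) = 0.0625 × 34 × 2 / 0.5 = 8.5, on 1 and N − 2 = 32 df
- power = 0.807, so n = 34 is reproduced. Other values of ρ give 66 (ρ = 0), 46 (0.3), 22 (0.7) and 16 (0.8).

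This is the formula for a time-by-arm test on one score measured twice, such as a difference score.

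**Inputs for the identity.** Two times, two trial types and two arms (9.4.2); 24 completers per arm (9.2); covariates age, sex and education (9.4.2).

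**Algebra.** Write A and B for the easier and harder trial type. For each participant the three-way contrast is

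(post B − pre B) − (post A − pre A) = (post B − post A) − (pre B − pre A).

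The right side is the change in the difference score. The interaction estimate is the arm difference in its mean. The split-plot error term (time × trial type × subject within arm) is the within-arm variance of the same quantity. Numerator, error term and df (1 and 48 − 2 = 46) therefore all match.

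**Numerical check.** In 500 simulated data sets of 48 with arbitrary covariance matrices, the raw-score three-way F and the F on the change in the difference score differed by at most 7 × 10⁻¹⁴ in relative terms. In one example both were 6.95431384 on 1 and 46 df. With three covariates, each entered with its within-subject interactions, both were 7.51508554 on 1 and 43 df.

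**What baseline adjustment gains.** Assumptions, since the documents give none of these: unit variances, A–B correlation 0.5 within a visit, test-retest correlation r for each trial type, and cross-visit A–B correlation 0.5r. Let D = B − A.

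- Var(D) = 1 + 1 − 2 × 0.5 = 1
- Cov(pre D, post D) = 2r − 2 × 0.5r = r
- Error variance of the planned test (change in D) = 2(1 − r)
- Error variance of post D adjusted for pre D = 1 − r²
- Ratio = (1 − r²) / [2(1 − r)] = (1 + r)/2

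The extra covariate costs a factor of about 42/41: with k covariates the variance of the arm effect is multiplied by 45/(45 − k), and k goes from 3 to 4.

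| r | (1 + r)/2 | × 42/41 | simulated, baseline D | simulated, baseline A and B |
|---|---|---|---|---|
| 0.5 | 0.75 | 0.77 | 0.78 | 0.80 |
| 0.6 | 0.80 | 0.82 | 0.80 | 0.83 |
| 0.7 | 0.85 | 0.87 | 0.87 | 0.89 |
| 0.8 | 0.90 | 0.92 | 0.91 | 0.94 |

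Closed form and simulation agree to within 0.02.

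**The case against.** **The identity has conditions.** The plan says repeated-measures analyses without naming an error term, and sections 6.2.4 and 8 foresee joint modelling and multiple imputation. This stands in part. A likelihood model could keep a participant who lacks one component score, and its test would then differ. The plan does not give that as its reason, however, and within each completed data set under multiple imputation all four cells are present and the identity holds. A random-intercept model with pooled error is also a different test. In simulation it gained about one point under compound symmetry (power 0.787 against 0.779), but once subject-by-time and subject-by-trial variance was present it was badly miscalibrated (type I error about 0, power 0.11 against 0.79). The plan does not specify such a model.

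**Nothing in the results changes.** This stands: keeping the planned test gives the same estimate, error rate and p value as the difference-score test.

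**Stronger readings.** A reader might infer that the double difference costs power against analysing the harder trial type alone. The documents do not support this. The two analyses have different estimands, and the ordering depends on c, the correlation between the changes in the two trial types, which is not given. With an assumed 0.8 SD effect confined to the harder condition, 24 per arm and unadjusted alpha 0.05, the double difference has 48% power at c = 0 and 99% at c = 0.8. The harder condition alone has 77% throughout, and the two are equal at c = 0.5.

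A reader might also infer that raw baseline scores would supply the missing power. The table shows otherwise: the gain comes from baseline adjustment, and under these symmetric correlations splitting the baseline into two raw scores is slightly less precise.

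**The plan limits covariates.** Section 9.4.2 calls more than the basic three infeasible. One baseline score per model costs one degree of freedom and, over the range shown, more than repays it.

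**Conclusion.** The point holds in this limited form. For three of the four named executive-function measures, the power advantage claimed for raw scores is zero, by algebra and without any assumption about correlations. It requires complete data and the standard repeated-measures error term. Letter Number Sequencing, which has no trial type, is unaffected.

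Nothing here shows the planned test to be invalid or its error rate wrong. The defect is that the plan claims a property its test does not have and passes over an adjustment that would bring a real gain. The size of that gain, a variance ratio of about 0.78 to 0.91, does rest on the assumed correlations and shrinks as test-retest correlation rises.

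**What to change.** In section 9.4.2:

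1. Delete the clause giving power as the reason for using raw scores.
2. For Trails, Stroop and Flanker, state that the post-visit difference score will be regressed on arm, adjusted for the same difference score at baseline plus age, sex and education. In a randomised comparison this targets the same arm difference as the planned interaction.
3. In the closing paragraph on covariates, add a sentence exempting an outcome's own baseline value from the limit.

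The cost is a few sentences and one degree of freedom per model, with no new data and no new tests. A separate test of the harder trial type should not be added as part of this change: it is a different estimand and would enlarge the Bonferroni family.

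If the sponsor prefers to keep the planned analysis, the minimum is to delete the power clause, or to name the model or estimand that would deliver the gain.

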Cognitive performance during the WWT – number of correct letters generated during WWT will be the main cognitive outcome. Additional cognitive/executive function tasks, including the WAIS-III Letter Number Sequencing Test (46), Stroop Color and Word Test (47), Trail Making Test (48) and Flanker Interference Task (49) will also be administered to determine if there are any far-transfer effects of our imagined gait intervention, and to carefully identify appropriate outcome measures for upcoming studies. Improved performance on the Stroop test following motor imagery training has been shown in individuals with Parkinson's disease (13), and we have previously shown improved performance on the Letter Number Sequencing Task in cognitively-healthy older adults following a cognitive intervention (50). Additional neuropsychological measures of processing speed, language, and memory will also be examined (see ee Clinicaltrials.gov-NCT02762604 for a comprehensive list).

Change in blood-oxygen-level-dependent (BOLD) signal will be examined during single (imagined walking) and dual task (imagined walking-while-talking) walking conditions. Changes in BOLD signal has been shown following physical and cognitive interventions in the past (51-53).

Additional variables/potential covariates will be recorded and carefully examined for potential inclusion as covariates or outcome measures in upcoming full-scale RCT, including stride length (cm), double support time (s), cadence (steps/min), swing time (s), stance time, stride length variability (SD), swing time variability (SD), the Geriatric Depression Scale (54), Medical Illnesses and Medication questionnaires (26, 55), Cognitive and Physical leisure activity questionnaire (56-58), Falls (59), Obesity (assessed with weight, waist circumference, and BMI (kg/m^2)), Vision (Snellen's chart), Disability (7 ADLs using the scale developed by Gill and colleagues (60, 61), IADL (62, 63), Blood pressure (Sitting/Standing), Gray Matter Volume/Atrophy (T1-Weighted structural images) White Matter Integrity (Diffusion Tensor Imaging; DTI) and White Matter Hyper intensities (Fluid-Attenuated Inversion Recovery; FLAIR).

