9.2 Sample Size and Randomization

The primary hypothesis examines change in gait speed (during NPW and WWT conditions). Setting an alpha level of .05, power of .80 and a medium effect size of defined as $f=.25$, the necessary sample size for detecting an interaction between time of test (pre and post), trial type (W or WWT) and imagery condition (Imagined gait or AC) is $n = 34$. Thus, our study completion goal of $n = 48$ (58 enrolled; 48 completed) is sufficient to detect our effects of interest and account for the 18% attrition rate expected during the study period (as observed in our previous studies (64)).

To detect a BOLD signal change at the individual subject level (i.e. first-level time-series modeling using SPM) at $p < 0.001$, a percent signal change of 0.34% is required using a published method and estimate of noise at a magnet strength of 3.0 Tesla (65). Based on this estimate, to detect a difference in contrast values between groups (i.e. second level analyses using SPM) at $p < 0.001$ and a power of at least .80, where the mean of one group's signal change is 50% of the other, 16 subjects per group are required. Thus, our study completion goal of $n = 48$ (24 in each condition) is sufficient to detect a main effect of imagery condition (imagined gait vs. AC) and leave room for the detection of interactions

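### Holm's step-down procedure could replace single-step Bonferroni for the behavioral analyses: same 0.05 family-wise control, never less power, a small gain in most settings

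*Combined protocol and SAP*

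**What the plan says.** Section 9.4.2 sets one multiplicity rule for the behavioral data: "All behavioral analyses will be corrected for multiple comparisons using the Bonferroni correction". No step-down or other sequential method is named or allowed anywhere in the document. The number of tests and the composition of the family are not given.

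The same section lists the additional executive-function measures: "Trail Making Test, the Letter Number Sequencing Test, the Stroop Color and Word Test, and the Flanker Interference Task". Section 9.1.2 adds a further candidate for the family: "number of correct letters generated during WWT will be the main cognitive outcome". It gives the additional tests two purposes, which are to look for far transfer and to help choose outcomes for later studies. Section 9.4.2 also explains that raw scores are analysed in place of difference scores for the sake of power.

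The only behavioral sample-size calculation is in section 9.2 and concerns gait speed: "Setting an alpha level of .05, power of .80 and a medium effect size of defined as $f=.25", used to obtain "the necessary sample size for detecting an interaction between time of test (pre and post), trial type (W or WWT) and imagery condition", with the result n = 34. The completion goal is 48, with 24 per group. No power is stated for any secondary behavioral test or at any Bonferroni-adjusted alpha.

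**The concern.** Single-step Bonferroni compares every p-value in a family of K tests with 0.05/K. Holm compares the smallest with 0.05/K, the next with 0.05/(K−1), and so on, and stops at the first failure. Holm needs no assumption that Bonferroni does not need. For decisions to reject or not, the method in the plan can therefore lose second and later rejections that Holm would allow at the same nominal error rate.

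This bears on a small pilot with several cognitive outcomes. Asking which of several measures respond is a question where second and later rejections count, and the plan already makes one analysis choice in order to gain power. What is at stake is modest: some efficiency in the adjusted tests.

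**Working it through.** **Inputs from the documents (sections 9.2, 9.1.2 and 9.4.2).** Alpha 0.05, power 0.80, f = 0.25, n = 34 needed, 48 completers, two equal groups; four named executive-function measures plus letters generated during WWT.

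**Assumptions, because the documents are silent.** K = 5 tests in the family (the four measures plus letters; K = 4 and 6 were also run). Correlation between tests 0 or 0.5. Correlation between repeated measures ρ = 0.5. All tests two-sided.

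**Step 1: the plan's own figure.** For a within-between interaction with two groups and m = 2 measurements, λ = N f² m/(1 − ρ), with 1 and N − 2 degrees of freedom. At N = 34, λ = 34 × 0.0625 × 2/0.5 = 8.5 and power is 0.807. The stated n = 34 is reproduced. It depends on ρ: the required N is 66 at ρ = 0, 46 at 0.3, 22 at 0.7 and 16 at 0.8. The multiplicity method does not enter this calculation, so neither 34 nor 48 changes.

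**Step 2: thresholds for K = 5.**

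| Ordered p-value | Bonferroni | Holm |
|---|---|---|
| smallest | 0.0100 | 0.0100 |
| 2nd | 0.0100 | 0.0125 |
| 3rd | 0.0100 | 0.0167 |
| 4th | 0.0100 | 0.0250 |
| largest | 0.0100 | 0.0500 |

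The first row is the same, so the chance of at least one rejection is the same under both methods. Every later Holm threshold is higher, so Holm rejects whatever Bonferroni rejects.

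**Step 3: gain at 80% unadjusted power per test.** The non-centrality is 1.960 + 0.842 = 2.80. The Bonferroni critical value at 0.05/5 is 2.576, so per-test power is Φ(2.80 − 2.576) ≈ 0.59. Both methods were applied to the same 200,000 simulated families per setting.

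| Real effects (of 5) | Average power per real effect, independent tests | Same, correlation 0.5 | Gain |
|---|---|---|---|
| 1 | 0.589 → 0.591 | 0.591 → 0.592 | about 0.1 point or less |
| 2 | 0.590 → 0.609 | 0.589 → 0.606 | about 2 points |
| 3 | 0.589 → 0.630 | 0.589 → 0.626 | about 4 points |
| 5 | 0.590 → 0.704 | 0.588 → 0.685 | 10 to 11 points |

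If all five effects are real, the chance of finding all five rises from 0.07 to 0.29 (independent) or from 0.24 to 0.48 (correlation 0.5). In no simulated family did Bonferroni reject where Holm did not.

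**Step 4: the same comparison at the protocol's f = 0.25.** With N = 48 and ρ = 0.5, λ = 48 × 0.0625 × 2/0.5 = 12. Power is 92.4% at 0.05 and 77.7% at 0.05/5. Moving from Bonferroni to Holm with K = 5 and independent tests gives 77.8% to 77.9% with one real effect, 77.6% to 79.7% with two, and 77.7% to 89.4% with five. For K = 4 and K = 6 the pattern is the same: about 0.1 point with one real effect, 2 to 4 points with two or three, and 8 to 13 points only if every effect in the family is real.

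**Step 5: realized error.** With two of five effects real and independent tests, the chance of any false rejection is about 0.03 under Bonferroni and 0.04 under Holm. Both are below 0.05. Holm gains its power by using more of the allowed error.

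**The case against.** The strongest reply is that this is a preference between two valid methods. Bonferroni is prespecified and controls the error rate, and no passages conflict. That stands: the choice is an inefficiency and not a mistake.

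A second reply is that the gain may be close to nothing. The additional tests look for far transfer, so effects on all of them cannot be presumed, and with one real effect Holm adds about 0.1 point. That also stands, and the 10 to 11 points should be read as an upper case. The family size, secondary effect sizes and correlations are all assumed.

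A third reply is that Bonferroni has matching simultaneous intervals and a lower realized error. Both are true. The plan does not mention simultaneous intervals, however, and Holm's error stays within the same 0.05 bound.

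Three stronger readings are tempting and are not supported:
- A reader might infer that real effects will be lost to the full-scale trial. The documents nowhere make adjusted significance the gate for choosing later outcomes.
- A reader might infer that only the secondary tests are affected. The sentence covers all behavioral analyses.
- A reader might infer that Holm cures the undefined family, or the contrast between this sentence and sizing at an unadjusted 0.05. It does not. Holm also needs a defined family, and its first step also uses 0.05/K.

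**Conclusion.** The point holds as a cheap optional improvement. For the decisions described in section 9.4.2, Holm is at least as powerful as single-step Bonferroni at the same nominal family-wise error, whatever the dependence between tests. It is more powerful only from the second rejection on.

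The direction of the result needs no assumption, but its size does. On five assumed tests at 80% unadjusted power, the realistic range with one to three real effects is roughly 0 to 4 points per real effect. The larger gains require every test in the family to have a real effect. It would be too much to say that Holm always adds power or that the plan's method is wrong.

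**What to change.** In section 9.4.2, name the Holm step-down procedure at family-wise alpha 0.05 in place of Bonferroni. State that it applies to all behavioral analyses within the family the sponsor defines, and report Holm-adjusted p-values. The sponsor must list the tests in that family for either method to be carried out.

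The cost is one sentence, with no more participants, data or visits. The change should be made before unblinded results are seen, since a later switch would look chosen for its result. The drawback concerns display: simultaneous intervals that match Holm are less simple. If Bonferroni intervals are kept, add that such an interval may include zero for an outcome that Holm rejects.

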Study Title

Motor Imagery: A Pilot Intervention for Improving Gait and Cognition in the Elderly

Objectives:

Primary. Compared to a visual imagery intervention group, participants who are enrolled in the motor imagery intervention (MI) group will demonstrate:

P1: Significant improvements in gait speed during actual Walking and Walking While Talking

Secondary. Compared to a visual imagery intervention group, participants who are enrolled in the motor imagery intervention (MI) group will show:

P 2.1: Significant improvements in cognitive performance during Talking and Walking While Talking

P 2.2: Change in blood-oxygen-level dependent signal during Walking and Walking While Talking

Design and Outcomes

The investigators propose to conduct a single-blind randomized clinical trial to test the efficacy of a phone-based motor imagery intervention for improving gait and cognition in older adults between 65 and 85 years old

[figure not shown]

Figure 1. Participant Flow

Interventions and Duration

Participants will be randomized into either a 12-week phone-based motor imagery intervention or visual imagery intervention (active control condition). Both groups will complete 36 (15-minute) sessions (9 hours).

Participants will receive gait, mobility, cognitive and neuroimaging assessments at baseline and post-intervention (14-18 weeks after intervention). Baseline and post-intervention assessments will last about 3 hours over 1 day.

Sample Size and Population

We will enroll 48 cognitively-healthy older adults (24 in each group).

STUDY TEAM ROSTER

Principal Investigator:

[name]
Einstein College of Medicine,
[name]
[contact]
[contact]

[contact]

Main responsibilities/Key roles: She will coordinate efforts between team members, supervise implementation of study measures and supervise data collection. She will develop data analysis plans as well as scientific presentations and manuscripts based on the research findings.

Mentor:

[name]
Albert Einstein College of Medicine,
[name]
[contact]
[contact]

[contact]

Main responsibilities/Key roles: He will be responsible for the oversight of [name] responsibilities and for establishing benchmarks to ensure successful completion of this intervention. He will also be involved in developing data analysis plans as well as scientific presentations and manuscripts based on the research findings.

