1.2 Secondary & Tertiary Objectives

Compared to a visual imagery intervention group, the participants who are enrolled in the motor imagery intervention group will show:

- Significant improvements in cognitive performance during Talking and Walking While Talking
- Changes in blood-oxygen-level dependent signal during Walking and Walking While Talking
- Improvement in executive function, and other mobility-related cognitive processes, such as speed of processing, memory and spatial navigation.
- Improved gait variability and other quantitative gait parameters during walking and walking while talking.

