function systems change as a function of our imagined gait versus the active control condition. This is also because changes in neural activation are often masked by between-subject variability, an issue that is particularly important to consider in aging populations (68, 69). Our multivariate analyses will be performed with software developed by my co-mentor in advanced neuroimaging analysis, [name]: http://www.nitrc.org/projects/gcva_pca. OrT-CVA will be used to identify covariance patterns in the fMRI signal as a function of trial type (iT, iW and iWWT) at each study visit (pre and post-intervention) for each imagery condition (imagined gait or AC). OrT-CVA is similar to other covariance analyses such as partial least squares (70, 71) in that it employs a principal components analysis (PCA) to the data matrix that is then transformed to a matrix of the experimental design. Linear regression is then applied to detect a covariance pattern, or ordinal trend, in the fMRI signal as a function of task conditions that is based on a linear combination of a small set of principal components. An ordinal trend is a monotonic change in pattern expression as a function of task conditions, in this case as a function of trial type (iW, iT and iWWT). The expression of an ordinal trend is quantified in terms of a participant-specific expression score that is derived by projecting the covariance pattern onto a participant's scan for each task condition. These participant-specific (or pattern) expression scores can also be used for further analysis (e.g. to correlate with actual WWT performance). Note that the proposed multivariate analyses of fMRI data involve data reduction and therefore does not involve multiple comparisons.

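### As written, the fMRI covariance patterns are derived within each visit and arm, and no between-arm test of BOLD change is specified

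*Combined protocol and SAP*

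**What the plan says.** The Précis lists as a secondary outcome, compared with visual imagery, "Change in blood-oxygen-level dependent signal during Walking and Walking While Talking". Section 1.2 repeats it, and Section 9.1.2 makes clear that the scanned tasks are the imagined ones. Section 9.4.2 gives a between-arm purpose for the imaging analysis: to learn how the locomotion and executive "systems change as a function of our imagined gait versus the active control condition".

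The method follows in the same section. "OrT-CVA will be used to identify covariance patterns in the fMRI signal as a function of trial type (iT, iW and iWWT", and this is to be done "at each study visit (pre and post-intervention) for each imagery condition (imagined gait or AC". A participant's expression score is "derived by projecting the covariance pattern onto a participant's scan for each task condition". The scores "can also be used for further analysis (e.g. to correlate with actual WWT performance", and that correlation is the only use named. The section closes the topic by saying that the fMRI analyses "involve data reduction and therefore does not involve multiple comparisons". The Bonferroni correction in Section 9.4.2 is limited to behavioral analyses.

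**The concern.** A covariance pattern is a set of voxel weights fitted to one data set. Patterns fitted in different cells have different weights, so a score of a given size does not mean the same thing in each. A post-minus-pre difference between two such scores reflects partly a change in how strongly the participant expresses a network and partly a change in which network is being scored. The same holds for a difference between arms.

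The second aim in Section 2.1 (Study Rationale) is that motor imagery strengthens the neural systems it engages. That needs a comparison between arms of change in one common quantity. If the SAP is followed as written, the analyst has up to four patterns, no rule linking them to scans, no test to run and no significance level, and so has to choose all of these after seeing the data. The multiplicity sentence would also let several pattern tests go uncorrected.

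**Working it through.** **1. The plan's own figure on this endpoint.** The OrT-CVA text gives no number. The only one is in Section 9.2: 16 per group for a between-group second-level SPM contrast at p < 0.001 with power 0.80. The between-subject SD is not given, so 16 can be neither confirmed nor refuted. It can only be inverted:

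- d = sqrt(2/n) x (z for alpha + z for power).
- Two-sided: sqrt(2/16) x (3.291 + 0.842) = 1.46 (1.61 with the t distribution).
- One-sided: 1.39 (1.51 with t).
- If the group difference is half of 0.34%, that is 0.17 points (an assumption), the implied SD is 0.17/1.61 = 0.106 to 0.17/1.39 = 0.122.

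This contrast does not fill the gap. Section 9.2 uses it for sizing a main effect of arm on signal, not a pre-post change, and Section 9.4 plans no SPM analysis.

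**2. Imaging and behavioral plans side by side.** For gait speed, Section 9.4.1 names the model, the factors and the interaction of visit, trial type and arm on which the inference rests. Section 9.4.2 does the same for the executive tests. For BOLD it names a method of finding patterns and an optional later use of scores. It gives no visit-by-arm term, alpha or inference procedure. This gap remains however the derivation sentence is read.

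**3. Number of derivations.** Two visits x two arms = 4 on the plain reading.

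**4. Multiplicity.** Assume each pattern is tested at 0.05 and the tests are independent (neither is stated in the plan):

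- four patterns: 1 - 0.95^4 = 18.5%;
- the two post-intervention patterns only: 1 - 0.95^2 = 9.75%;
- four patterns at the 0.001 used for sizing in Section 9.2: 1 - 0.999^4 = 0.4%.

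Pre and post scans come from the same people, so independence will not hold exactly. At 0.05 each, the four-test figure lies between 5% (complete dependence) and 4 x 0.05 = 20% (Bonferroni bound).

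**5. Illustrative simulation.** Assumed settings: 24 per arm, 200 voxels, three ordered tasks, six principal components, and the same population in all four cells, so there is no true arm difference. There were 500 runs per signal strength. The arm test compared change in the slope of expression over the tasks, at nominal 5%.

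| Signal strength | Mean absolute cosine between cell patterns | Rejection, cell-specific patterns | Rejection, one pooled pattern |
|---|---|---|---|
| 0 | 0.07 | 0.4% | 4.8% |
| 1 | 0.06 | 2.4% | 6.6% |
| 2 | 0.32 | 8.6% | 4.2% |

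The Monte Carlo standard error at 5% is sqrt(0.05 x 0.95/500) = 1.0 point. The pooled-pattern results agree with 5% to within two standard errors; the cell-specific results do not. Patterns fitted to identical populations overlapped little. The pooled pattern used the scans of both visits; a baseline-only pattern was not simulated.

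**The case against.** The text never says that the patterns are derived separately, nor that there are four. It also speaks of the data matrix and the covariance pattern in the singular, so one derivation with visit and arm as design factors is a possible reading. That stands: separate derivation is the plain reading, not the plan's own word. But a pooled derivation is nowhere stated, and even under it no visit-by-arm test is named.

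A reader might go further and infer that a spurious arm difference is likely. The simulation does not support this. The rejection rate was below nominal in two settings and 8.6% in the third, so the trouble is poor calibration and unclear meaning, not a general excess of false positives.

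A reader might also suppose that arms will be compared by whether each shows a significant pattern. With equal true effects and 80% power in each arm, exactly one would be significant 2 x 0.8 x 0.2 = 32% of the time, half of that (16%) favoring motor imagery. The plan proposes no such rule, so this is a hazard of leaving the test open, not a property of the stated analysis.

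The multiplicity sentence is correct for voxelwise comparisons. Two of the four patterns are baseline patterns, so finding one there by chance is not a false claim about the intervention. Finally, Section 2.1 predicts that the two conditions engage different systems, so arm-specific patterns have a descriptive use.

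**Conclusion.** The point holds as a defect of specification with a real consequence. Following the plain text of Section 9.4.2 gives cell-specific scores without a common scale and no test of the arm difference in BOLD change, although that is a stated secondary objective. The absence of the test is certain from the text. The lack of a common scale rests on the plain reading of the derivation sentence.

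The 18.5% is illustrative only, since it assumes an alpha and independence that the plan does not give. The simulation shows direction, not size, because its signal, noise and dimensions are assumed.

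It would go too far to say that the second aim cannot be answered. The scans are to be collected, the between-arm intent is written down, and the scores are available for further analysis; what is missing is the choice of pattern and test. For a secondary outcome in a pilot this should be corrected before imaging data are analyzed, but it does not touch the gait-speed analysis.

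**What to change.** In Section 9.4.2:

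- Derive one iW/iT/iWWT pattern from the baseline scans of all participants, pooled and blind to arm. Sections 4.3 and 6.2.2 place randomization after the baseline assessments, so treatment cannot have shaped this pattern.
- Project that pattern onto every pre and post scan. Summarize each visit as one number per participant, for example the slope over the three tasks.
- Make the main imaging comparison the arm effect on post expression, adjusted for baseline expression, age, sex and education. State alpha, and a permutation or bootstrap procedure for the pattern itself.
- Do not interpret within-arm change on this score. The pattern is fitted to the baseline scans, so baseline expression is flattered, though without regard to arm.
- Label visit- or arm-specific patterns exploratory. If they are tested formally, adjust for their number (0.05/4 = 0.0125 for four).
- Limit the multiplicity sentence to voxelwise comparisons.
- Confirm that both arms perform iW, iT and iWWT in the scanner at both visits. Section 2.1 (Study Rationale) describes this for participants generally, but Section 5.1 also describes an object-imagery protocol in the MRI, and the two must be reconciled. If controls did only object imagery, the ordered trend would not exist in that arm.

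The cost is SAP wording; no added scans or participants are needed. The downside is that a pattern that emerges only after training will be seen only in the exploratory analysis.
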